4.5 Entry Criteria

The following eligibility criteria were designed to select patients for whom the protocol treatment is considered appropriate. All relevant medical and non-medical conditions should be taken into consideration when deciding whether this protocol is suitable for a particular patient. Eligibility criteria may not be waived by the investigator.

4.5.1 Inclusion Criteria

In order to be eligible for participation in this trial, the patient must:

1. Have treatment naive and histologically confirmed high-/intermediate-risk LA-SCCHN
2. Be willing and able to provide written informed consent for the trial.
3. Be ≥ 18 years of age on day of signing informed consent.
4. Have measurable disease based on RECIST 1.1.
5. Have provided tissue from an archival tissue sample or newly obtained core or excisional biopsy of a tumour lesion.
6. Have a performance status of 0 or 1 on the ECOG Performance Scale.
7. Be fit for definitive platin-based chemoradiation therapy.
8. Demonstrate adequate organ function as defined in table 1, all screening labs should be performed within 10 days of confirmation of study eligibility.

System	Laboratory Value
Haematological	
• Absolute neutrophil count (ANC)	$\geq 1,500$ /mcL
• Platelets	$\geq 100,000$ / mcL
• Haemoglobin	≥ 9 g/dL or ≥ 5.6 mmol/L
Renal	
• Serum creatinine OR • Measured or calculated ^a creatinine clearance (GFR can also be used in place of creatinine or CrCl)	$\leq 1.5 \times$ upper limit of normal (ULN) OR ≥ 60 mL/min for patient with creatinine levels $> 1.5 \times$ institutional ULN
^a Creatinine clearance should be calculated per institutional standard.	
Hepatic	
• Serum total bilirubin OR • Direct bilirubin	$\leq 1.5 \times$ ULN OR \leq ULN for patients with total bilirubin levels > 1.5 ULN
• AST (SGOT) and ALT (SGPT)	$\leq 2.5 \times$ ULN OR $\leq 5 \times$ ULN for patients with liver metastases
Coagulation	
Prothrombin Time (PT)	$\leq 1.5 \times$ ULN unless patient is receiving anticoagulant therapy as long as PT or PTT is within therapeutic range of intended use of anticoagulants
Activated Partial Thromboplastin Time (aPTT)	$\leq 1.5 \times$ ULN unless patient is receiving anticoagulant therapy as long as PT or PTT is within therapeutic range of intended use of anticoagulants

Table 1: Adequate Organ Function Laboratory Values

9. Female patient of childbearing potential should have a negative urine or serum pregnancy within 72 hours prior to confirmation of study eligibility. If the urine test is positive or cannot be confirmed as negative, a serum pregnancy test will be required.
10. Female patient s of childbearing potential should be willing to use 2 methods of birth control or be surgically sterile, or abstain from heterosexual activity for the course of the study through 120 days after the last dose of study medication (Reference Section 6.7.2). Patient s of childbearing potential are those who have not been surgically sterilized or have not been free from menses for > 1 year.
11. Male patient s should agree to use an adequate method of contraception starting with the first dose of study therapy through 120 days after the last dose of study therapy.

4.5.2 Patient Exclusion Criteria

The patient must be excluded from participating in the trial if the patient:

1. Is currently participating in or has participated in a study of an investigational agent or using an investigational device within 4 weeks of the first dose of treatment.
2. Has received prior radiotherapy to the head and neck region.
3. Has a diagnosis of immunodeficiency or is receiving systemic steroid therapy or any other form of immunosuppressive therapy within 7 days prior to the first dose of trial treatment.
4. Has had a prior monoclonal antibody, chemotherapy, targeted small molecule therapy, or radiation therapy.
5. Has a known additional malignancy that is progressing or requires active treatment. Exceptions include basal cell carcinoma of the skin, squamous cell carcinoma of the skin, or in situ cervical cancer that has undergone potentially curative therapy.
6. Has known active central nervous system (CNS) metastases and/or carcinomatous meningitis. Patient s with previously treated brain metastases may participate provided they are stable (without evidence of progression by imaging for at least four weeks prior to the first dose of trial treatment and any neurologic symptoms have returned to baseline), have no evidence of new or enlarging brain metastases, and are not using steroids for at least 7 days prior to trial treatment.
7. Has an active autoimmune disease requiring systemic treatment within the past 3 months or a documented history of clinically severe autoimmune disease, or a syndrome that requires systemic steroids or immunosuppressive agents. Patient s with vitiligo or resolved childhood asthma/atopy would be an exception to this rule. Patients that require intermittent use of bronchodilators or local steroid injections would not be excluded from the study. Patient s with hypothyroidism stable on hormone replacement or Sjogren's syndrome will not be excluded from the study.
8. Has evidence of interstitial lung disease or active, non-infectious pneumonitis.
9. Has an active infection requiring systemic therapy.
10. Has active tuberculosis.

11. Has known hypersensitivity to pembrolizumab or any of its excipients.
12. Has a history or current evidence of any condition, therapy, or laboratory abnormality that might confound the results of the trial, interfere with the patient's participation for the full duration of the trial, or is not in the best interest of the patient to participate, in the opinion of the treating investigator.
13. Has known psychiatric or substance abuse disorders that would interfere with cooperation with the requirements of the trial.
14. Is pregnant or breastfeeding, or expecting to conceive or father children within the projected duration of the trial, starting with the pre-screening or screening visit through 120 days after the last dose of trial treatment.
15. Has received prior therapy with an anti-PD-1, anti-PD-L1, anti-PD-L2, anti-CD137, or anti-Cytotoxic T-lymphocyte-associated antigen-4 (CTLA-4) antibody (including ipilimumab or any other antibody or drug specifically targeting T-cell co-stimulation or checkpoint pathways).
16. Has a known history of Human Immunodeficiency Virus (HIV) (HIV 1/2 antibodies).
17. Has known active Hepatitis B (e.g., HBsAg reactive) or Hepatitis C (e.g., HCV RNA [qualitative] is detected).
18. Has received a live vaccine within 30 days prior to the first dose of trial treatment.

5.0 STUDY PLAN AND PROCEDURES

5.1 Study Schedule

Whilst on this treatment patients will be assessed at the administration of the pre-loading dose and then every 3 weeks at the administration of their next dose of pembrolizumab for a total of 8 doses or until they progress, suffer unacceptable toxicities, withdraw or the study ends. After the last dose of pembrolizumab patients will be required to attend post-treatment follow-up visits as described below and/or safety follow-up (SFU) visit at 12 weeks or before the initiation of a new anti-cancer therapy, whichever comes first.

If the patient has completed all 8 doses of pembrolizumab and has not progressed or discontinued treatment for any other reason they will be seen at 4 weeks and 8 weeks after the last dose of pembrolizumab for the post treatment follow up visit. They will then return at 12 weeks for the SFU and after this be followed up every 4 weeks for 9 months or until disease progression, initiation of a new anti-cancer therapy, death, withdrawal, end of the study.

If the patient has not progressed but discontinued treatment for another reason they will be seen 8 weeks after the last dose of pembrolizumab for the post treatment follow up. They will then return at 12 weeks for the SFU and after this be followed up every 8 weeks for 9 months until disease progression, initiation of a new anti-cancer therapy, death, withdrawal or end of the study.

Patients that have progressed or initiated a new anti-cancer therapy during treatment or follow-up phase will enter into the survival follow-up phase and will be contacted every 12 weeks to assess for survival status until death, withdrawal of consent, or the end of the study, whichever occurs first. Patients that progress during treatment will be required to have a SFU at 12 weeks or before the initiation of a new anti-cancer therapy; whichever comes first.

The schedule of study assessment (Table 2) summarises the trial procedures to be performed at each visit. Individual trial procedures are described in detail below. It may be necessary to perform these procedures at unscheduled time points if deemed clinically necessary by the investigator.

Furthermore, additional evaluations/testing may be clinically indicated for reasons related to patient safety. In some cases, such evaluation/testing may be potentially sensitive in nature (e.g., HIV, Hepatitis C, etc.). Such evaluations/testing will be performed in accordance with local regulations.

Trial Period:		Screening Phase	Treatment Cycles – Every 3 Weeks												End of Treatment - At time of discontinuation of treatment ⁴	Post-Treatment							
Treatment Cycle/Week Title:			Pre-Loading Dose	C 1	C 2	C 3	C 3	C 3	C 4	C 4	C 4	C 5	C 6	C 7		Post-Treatment Follow-up (A) ¹	Post-Treatment Follow-up (B) ²	Safety Follow-up (SFU)	Post-Safety Follow-up (A) ¹	Post-Safety Follow-up (B) ²	Survival Follow-up		
Scheduling Window (Days):				Wk 0	Wk 3	Wk 6	Wk 7 ⁸	Wk 8	Wk 9	Wk 10	Wk 11	Wk 12	Wk 15	Wk 18		4 wks and 8 wks from last dose of Pembrolizumab	8 wks from last dose of Pembrolizumab	12 wks from last dose of Pembrolizumab ³	Every 4 wks from SFU for 9 months	Every 8 wks from SFU for 9 months	Every 12 wks from progression / initiation of anti-cancer treatment		
Administrative Procedures																							
Informed Consent	X																						
Inclusion/Exclusion Criteria	X																						
Demographics, Medical & Treatment History, Smoking Status	X																						
Anti-cancer therapy Review																X	X	X	X	X			
Survival / Disease Status																X	X	X	X	X	X		
Clinical Procedures / Assessments																							
Review Adverse Events		X	X	X	X	X		X	X	X	X	X	X	X	X	X	X	X	X				
Radiation Toxicity Review				X	X			X	X	X	X	X	X	X	X	X	X	X	X	X			
Prior and Concomitant Medication Review	X	X	X	X	X			X	X	X	X	X	X	X	X	X	X	X	X				
Full Physical Exam	X																						
Directed Physical Exam		X	X	X	X	X		X	X	X	X	X	X	X	X	X			X				
Vital Signs, Weight & ECOG	X	X	X	X	X			X	X	X	X	X	X	X	X				X				
Height	X																						
Pregnancy Test – Urine/Serum	X																						
T3, T4, TSH, PT and aPTT	X			X		X			X		X		X						X				
Haematology & Biochemistry	X	X	X	X	X			X	X	X	X	X	X	X	X				X				
Urinalysis	X																						
Admin of Pembrolizumab		X	X	X	X				X			X	X	X									
Admin of Radiotherapy			X	X	X	X																	
Admin of Chemotherapy			X	X	X																		
Tumour Imaging	X													X ⁷									
Clinical disease assessment	X		X	X	X			X			X	X											
Archival collection or new tumour biopsy	X		X ⁵	X ⁵																			
HPV testing (p16 Immunohistochemistry)	X																						
Research Blood Collection (OPTIONAL)	X			X				X			X				X ⁶								
Neck dissection																							

1. For patients who have completed 8 doses of pembrolizumab and have not progressed or discontinued from unacceptable toxicities.

2. For patients that have discontinued treatment for any reason other than progression and have not withdrawn consent for participation.

3. Or before the initiation of a new anti-cancer therapy whichever comes first.

4. Only applicable if patients come off between on treatment visit cycles.

5. Where feasible and if the patient has consented OPTIONAL post-treatment research tumour biopsies will be taken at week 0 and week 3.

6. In patients with N+ Disease.

7. CT / MRI Imaging should be completed at screening, Week 15 (Cycle 6) and then every 12 weeks for 12 months or until disease progression, discontinuation or initiation of another anti-cancer treatment.

8. C3 Wk 7 is not a clinic visit. Patient will continue to receive radiotherapy only.

Table 2: Schedule of Study Assessment

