Patients who discontinue pembrolizumab for any reason other than disease progression will move into the post-safety follow-up (B) phase. These patients will be assessed every 8 weeks from SFU for 9 months or until the patient suffers disease progression, they begin a new anti-cancer treatment or they withdraw. Each follow-up visits will monitor disease status and assess for any new anti-cancer therapies initiated. If a patient progresses or begins a new anti-cancer therapy they will move to the survival follow-up phase.

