5.3.9 Tumour Imaging and Assessment of Disease

5.3.9.1 Clinical Assessment.

Patients will be assessed clinically for disease resolution at screening and then every 3 weeks until 8 weeks post-chemoradiotherapy. These clinical assessments will include direct visualisation of the upper aerodigestive tract (including flexible nasendoscopy) and clinical examination of the neck.

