5.3.9.3 Timing and Assessment of Disease

Tumour imaging may be performed by CT or magnetic resonance imaging (MRI), but the same imaging technique should be used in a patient throughout the trial. The initial tumour imaging will be performed no more than 28 days prior to confirmation of eligibility. Scans performed as part of routine clinical management are acceptable for use as the screening scan if they are of diagnostic quality and performed within the correct time window.

On-study imaging will be performed at screening then at cycle 6 to assess disease response. After cycle 6 imaging will be performed every 12 weeks for 12 months and should follow calendar days and should not be adjusted for delays in cycle starts or extension of pembrolizumab cycle frequencies.

Local investigator assessment with site radiology will be used to determine eligibility and for patient management. Tumour imaging and assessment per local standard of care should be performed for patient management, and may include additional imaging (e.g. bone scan for lung cancer patients).

Imaging should continue to be performed until documented disease progression, the start of new anti-cancer treatment, withdrawal of consent, death, or the end of the study, whichever occurs first.

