8.2.5 Data analysis

All quantitative data will be presented as number of observations, means and SDs for normally distributed data or as median and interquartile ranges for data that appear to be non-normally distributed. Qualitative data will be presented as number of observations and frequencies. When appropriate, data will be presented together with 95% confidence intervals. All statistical tests will be two-tailed and a p-value <0.05 (5%) will be considered as achieving statistical significance. The analysis will be performed separately in HPV-ve and HPV+ve cohorts, respectively.

- Baseline characteristics will be summarized using descriptive statistics. Dose limiting toxicity will be summarized using overall frequencies. Incidence (highest grade) of side effects of radiotherapy (CTCAE scale v 4.0, for acute side effects and LENT SOMA for late radiotherapy scoring systems) will be reported.
- Duration of clinical benefit will be calculated as the number of patients who had a best overall response of CR, PR, or SD according to the RECIST criteria until the first date of recurrence or progressive disease (PD) and will be measured at the landmark points in the study **6 months, 1 year and 2 years, respectively**. They will be presented as proportions and 95% confidence intervals will be reported if appropriate.
- Progression free and overall survival will be determined using Kaplan-Meier methods **presenting the median survival times, and survival rates will be reported at 6 months, 1 and 2 years, respectively**. Overall survival will be measured from date of treatment to date of death from any cause; surviving patients will be censored at date last known to be alive. Progression free survival will be measured from start of treatment to date of first appearance of disease progression, relapse or death from any cause. Patients alive without progression or relapse will be censored at date last known to be alive. Survival curves will be estimated for each HPV cohort and compared using the log-rank test.

- The levels of CD4, CD8, T regulatory cell (CD4/CD25, FOXP3), B cells, NK cells and Circulating free tumour DNA pre RT, during RT and post RT will be presented as descriptive statistics according to their HPV status. The expression of PD1 (and other immune exhaustion markers) on immune cells and PDL1 on tumour cells will be presented as descriptive statistics.

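### Table 2 footnote 7 lists discontinuation as a reason to stop CT/MRI and section 5.3.9.3 does not, so patients who stop pembrolizumab early may accrue progression-free time without scans

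*Combined protocol and SAP*

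**What the plan says.** Footnote 7 of Table 2 (section 5.1) places CT or MRI at screening, at week 15 (cycle 6) and then "every 12 weeks for 12 months or until disease progression, discontinuation or initiation of another anti-cancer treatment".

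Section 5.3.9.3 has a different stopping list. Under it, scans "should continue to be performed until documented disease progression, the start of new anti-cancer treatment, withdrawal of consent, death, or the end of the study". Discontinuation is not on it, and the same section says the later scans "should follow calendar days and should not be adjusted for delays in cycle starts or extension of pembrolizumab cycle frequencies". The Trial Summary also gives 12-weekly scans for 12 months with no stop at discontinuation.

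For patients who stop early, section 3.5.6 says: "Patients who discontinue pembrolizumab for any reason other than disease progression will move into the post-safety follow-up (B) phase". Those visits are 8-weekly for nine months from the safety follow-up and monitor disease status by no stated method. Section 5.2.5, on the survival/disease status assessment, describes only survival, death and loss to follow-up. On examination, section 5.3.9.1 says: "Patients will be assessed clinically for disease resolution at screening and then every 3 weeks until 8 weeks post-chemoradiotherapy". That includes nasendoscopy and examination of the neck.

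The PFS rule in section 8.2.5 is: "Patients alive without progression or relapse will be censored at date last known to be alive".

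**The concern.** Two current rules disagree on whether a patient who stops pembrolizumab without progression goes on being scanned. Such patients are foreseeable, because Table 10 in section 6.3.9.2 provides for permanent discontinuation for a range of toxicities. They are also unlikely to be a random sample with respect to outcome.

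If imaging ends when treatment ends, PFS and RECIST best response lose their main measurement in this subgroup. The censoring rule then adds to the problem. It runs to the last date known alive, not to the last time disease was assessed, so the patient stays in the risk set as progression-free however little has been looked for. The secondary estimates at 6 months and 1 year are at stake, as is the response classification behind clinical benefit.

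**Working it through.** **1. What discontinuation means in footnote 7.** Three things favour the treatment reading:
- A column of the same table is headed "End of Treatment - At time of discontinuation of treatment".
- Footnote 2 separates stopping treatment from withdrawing consent.
- Sections 6.9 and 6.10 separate discontinuing medication from withdrawing from the study.

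Against it, sections 3.6, 4.4 and 6.10 each use the verb for leaving the study or trial. The treatment reading is the better supported, but it is not certain.

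**2. Scan calendar.** Inputs from sections 3.2 and 5.3.9.3 and Table 2: pre-loading dose at week −2, cycle 1 at week 0, cycles every 3 weeks, first post-baseline scan at week 15, then every 12 weeks for 12 months (taken as 52 weeks, to week 15 + 52 = 67). Scan weeks are 15 + 12k, up to 67: weeks 15, 27, 39, 51 and 63.

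| Last dose, stopped early without progression | Scans under footnote 7 (treatment reading) | Scans under 5.3.9.3 |
|---|---|---|
| Pre-loading to cycle 5 (weeks −2 to 12) | 0 | up to 5 |
| Cycle 6 (week 15) | 1 | up to 5 |

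**3. Scans before the PFS landmarks.** Taking the pre-loading dose as start of treatment, 6 months is about week 26 − 2 = 24 and 1 year is week 52 − 2 = 50. Under 5.3.9.3, one scan (week 15) precedes the 6-month landmark and three (weeks 15, 27 and 39) precede the 1-year landmark. Under footnote 7, a patient who stops at or before cycle 5 has none before either.

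**4. One patient followed through.** Last dose at cycle 3, week 6:
- Post-treatment (B) visit at week 6 + 8 = 14 and safety follow-up at week 6 + 12 = 18.
- Post-safety (B) visits at weeks 26, 34, 42 and 50. The last is 52 weeks after the pre-loading dose.
- Chemoradiotherapy lasts 7 weeks, so scheduled endoscopic and neck assessment ends at about week 7 + 8 = 15.

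From about week 15 to week 50 there is scheduled contact but no scheduled scan or endoscopy, yet the patient can count as progression-free at 6 months and to about 1 year. The nine-month (B) phase closes at about week 18 + 39 = 57, so the week-63 scan falls after it. That is one reason the table says up to five.

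**5. Size.** The plan states no PFS rate and no discontinuation rate, so there is no figure to reproduce. From the sample size alone (section 8.2.4, at most 18 per HPV cohort), one unrecorded progression moves a crude landmark proportion by 1/18 = 5.6 points.

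As an illustration on assumed inputs only, upward bias ≈ d × (1 − S) × u. Here S is true landmark PFS, d is the share who stop early unscanned, and u is the share of their PFS events that are progressions still unrecorded at the landmark. Deaths and clinically detected recurrences lower u.
- S = 0.60, d = 0.20: 0.20 × 0.40 × 0.25 = 2 points; with u = 0.5, 4 points.
- Lowest combination tried: 0.10 × 0.20 × 0.25 = 0.5 points.
- Highest with u = 0.5: 0.30 × 0.50 × 0.5 = 7.5 points.
- With u = 1: 0.30 × 0.50 × 1 = 15 points. This is a ceiling, because it requires that none of these patients' events be a death or be found clinically.

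The formula treats these patients as followed past the landmark. Those who stop before cycle 3 have their last scheduled (B) visit 44 to 49 weeks after the pre-loading dose, so at 1 year it is only approximate.

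**The case against.** The case for leaving this as a minor wording matter has real strength.

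- *The word is ambiguous.* If discontinuation means leaving the study, the footnote roughly matches withdrawal of consent in 5.3.9.3 and little conflict remains. Treatment ends at week 18 even for completers, so most of the 12-month calendar lies after the last dose in any case. This stands as a reason to settle the wording. It does not make the wording safe.
- *The detailed text may govern.* Section 5.1 says Table 2 summarises procedures described more fully below it, and there is a single site. A reader might infer that the footnote will be applied; the documents do not establish that. However, sections 3.5.2 and 3.5.3 refer the post-treatment visits to Table 2, and no order of precedence is stated.
- *Early stoppers are still seen.* A reader might infer that they have no disease assessment. That is not so. The protocol provides weekly visits for four weeks after chemoradiotherapy, nasendoscopy and neck examination to about week 15, the (B) and safety visits, neck dissection where feasible in node-positive disease, and local standard-of-care imaging. What may be missing is uniform, scheduled radiological assessment.
- *The table may be damaged.* The imaging row shows no mark in the post-treatment columns of the text available, but that may be a PDF-reading artefact. No weight is put on it.
- *Differential bias between HPV cohorts.* A reader might infer that the log-rank comparison is distorted. Section 3.1 says only that toxicities may differ, so this is speculation.

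**Conclusion.** The inconsistency is real and worth correcting. On the better-supported reading, footnote 7 removes every scheduled post-baseline scan from a patient who stops pembrolizumab without progression before week 15, where 5.3.9.3 provides up to five. Combined with censoring at last known alive, PFS at 6 months and 1 year may be biased upward, and RECIST best response may lack a scheduled scan.

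This depends on the footnote being followed in its treatment sense, on some patients stopping early, and on some of their progressions not being picked up clinically or on routine scans. A reader might conclude that PFS is overstated, or quote a number of points. The documents support neither: no input to the size comes from them, deaths still count as events, and these patients are censored, not scored as successes. PFS and response are secondary, and the MTD/DLT primary endpoint is untouched.

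**What to change.** Reconcile footnote 7 with section 5.3.9.3. For the endpoints, the direct way is to replace discontinuation in the footnote with the stopping list 5.3.9.3 already uses: documented progression, new anti-cancer treatment, withdrawn consent, death, or end of study. Add a sentence that patients who stop pembrolizumab without progression stay on the same imaging calendar (week 15, then 12-weekly for 12 months), including any scan that falls after their last (B) visit. Check that the post-treatment columns of the original Table 2 agree.

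As a companion change in 8.2.5, censor PFS for patients alive without progression at the last adequate tumour assessment, and define what counts as adequate. The two changes belong together. Changing the censoring rule alone could censor an unscanned patient close to baseline, which discards follow-up and leaves the loss informative.

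The cost is one footnote, one sentence and one SAP line in an amendment. The scans are already planned in 5.3.9.3. The only downside is a few scans that someone working from Table 2 alone would have omitted.
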